**Version #3**

**Date: September 19, 2017**

**pg. 4**

recording as well as status and duration of recording. Recording will default to three (3) hour durations and can be extended from the control panel. All recordings will be managed by a video recording server and stored on network accessible server storage space. All videos will be labeled by date, time and bed space at which the recording took place. Staff can then log into the server and review videos to ensure proper intubation procedures have been followed and to improve training methods.

Below is a technical workflow diagram:

1. User accesses control panel to select camera at bed space. Control panel sends signal to recording server to start recording on requested camera.
2. Recording server requests video from camera.
3. Camera starts sending video and audio data to recording server.
4. Recording server stores video and audio data on video storage server.
5. Staff can then access recorded data directly from the video storage server.

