## **Abstract**

Tracheal intubation of infants and children is a critical lifesaving skill, and its importance is recognized by the Accreditation Council on Graduate Medical Education (ACGME), Residency Review Committee (RRC), the Neonatal Resuscitation Program (NRP) and Pediatric Advanced Life Support (PALS) programs. Despite its importance, current training is lacking in teaching this critical procedural skill as demonstrated by the inability of up to 1/3 of upper level Pediatric residents to be able to successfully intubate Very Low Birth Weight (VLBW, <1500 grams) neonates. New technology, which has now been adapted to the existing telemedicine network in Arkansas, offers an exciting opportunity to improve the ability of pediatric trainees to accomplish this critical task. We will utilize a deliberate practice approach with immediate feedback during neonatology rotations using the Storz video laryngoscope to teach this critical skill to Pediatric and Med-Peds residents (n=95 residents total). Previous work demonstrated improvement in skills with a manikin, but it is unknown if these skills will translate to live intubations. The residents will receive training during alternating months, and will be recorded during live intubations. We will assess how intubation skills using a manikin translates to live patients. We anticipate this training will dramatically improve intubation skills and resident confidence as evidenced by intubation accuracy.

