### **Hypothesis and/or Specific Aims or Objectives**

Specific Aim 1. *Assess the impact of this educational manikin intervention on live patients.*

We hypothesize learners in the Intervention Group vs. the Control Group will have enhanced success in intubation as determined by the number of attempts and time required for intubation of live patients.

Specific Aim 2. *Assess the satisfaction of this educational intervention and equipment.*

We hypothesize pediatric residents will have increased satisfaction scores and confidence for intubating live patients in the Intervention Group vs. the Control Group.

Specific Aim 3. *Assess the association of confidence in intubation with actual success in intubation.*

We hypothesize increased confidence will be associated with increased intubation success.

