## **Methods**

This research study will include 95 resident physicians. We anticipate 80 residents will enroll, similar to our previous study in which 82 residents participated. Residents will be randomized to the Intervention Group or the Control Group. This study will be explained to potential participants as they begin their assigned rotation to the Neonatal Intensive Care Unit (NICU). The explanation of the study and the Information Sheet will be introduced during the first five (5) days of this rotation. Residents will be allowed to ask any questions they feel necessary and take as much time as needed in order to make a fully informed voluntary consent. It will be explained that their participation in this study is completely voluntary and a decision to not participate will have no impact on their training or standing in the residency program. Randomization will occur by the month the resident is assigned to the NICU.

All participants will:

- Receive NRP training and certification offered at the beginning of their residency
- Complete a Baseline Survey
- Complete a Baseline Cognitive and Simulation Assessment
- Have a Stabilization Room video recording as part of the quality improvement process for neonatal resuscitation
- Complete a Cognitive and Simulation Assessment at the end of the month
- Complete an End of Rotation Survey

Residents who are randomized to the Intervention Group will, in addition:

- Observe a 7 minute NRP video
- Complete a hands-on intubation simulation with [name] instructing:
  - Using state of the art technology, a Storz C-MAC video laryngoscope
  - Identifying anatomical landmarks
  - Practice on the manikin until intubation occurs within 15 seconds

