During the monthly rotation of each resident, ongoing data will be collected on the residents' ability to successfully intubate on the first attempt, the total number of attempts to intubate, and the total number of successful attempts at intubating a neonate within 30 seconds, the time limit set by NRP. All live intubations performed in the Stabilization Rooms will be recorded and reviewed by designated members of the NICU Safety Committee. The recorded videos of study participants will also be reviewed by [name] and [name], R.N. The information obtained from the video recordings will be kept in a safe, secure file that is password protected. At the end of the monthly rotation each resident, including those in the Control Group, will be offered the opportunity to complete the Hands-on Intubation training simulation with [name].

Angel Eye Cameras and control modules will be placed on the patient beds in the NICU Resuscitation Rooms which will be used for recording and monitoring infant intubation procedures. The cameras will be placed on the bed above the infant and staff while the control panel will be on a nearby wall to allow for easy starting and stopping of recording and monitoring of recording during the procedure. The control panel will have access to start/stop

[figure not shown]

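### Arm follows calendar month and intubation videos are filed by date, so a reader who knows the schedule can infer the arm, and no masked scoring is provided for

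*Protocol*

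**What the plan says.** **Allocation.** Protocol, Methods: "Randomization will occur by the month the resident is assigned to the NICU". Protocol, Abstract: "The residents will receive training during alternating months, and will be recorded during live intubations".

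**Recording and review.** Protocol, Methods: "All live intubations performed in the Stabilization Rooms will be recorded and reviewed by designated members of the NICU Safety Committee". It continues: "The recorded videos of study participants will also be reviewed by" two named people (names removed), at least one of them a nurse. The recording workflow on pg. 4 adds: "All videos will be labeled by date, time and bed space at which the recording took place". Its last step has staff open recordings directly on the storage server.

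**Outcomes.** Aim 1 defines success on live patients as "determined by the number of attempts and time required for intubation of live patients". Methods lists first-attempt success, total attempts, and successes within the 30-second NRP limit. The SAP compares overall and first-time success between arms by logistic regression, and success counts by negative binomial regression. It does not analyse seconds as a separate variable. No outcome is designated primary.

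**Coding.** Data Handling and Recordkeeping gives participants' documents a unique code. It does not extend that code to the videos.

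**Not stated in either document.** Masking of video readers, relabelling of clips, the timing of scoring relative to the rotation, and definitions of an attempt, of success, or of when the 30-second clock starts and stops.

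**The concern.** All residents rotating in a given month share an arm, so a date is as informative as an arm label to anyone who knows which months had training. The outcomes leave room for judgement: whether a re-inserted blade is a new attempt, when an attempt begins and ends, and whether the tube was in place just before or just after 30 seconds. The Protocol's Abstract expects a dramatic improvement from the training. A reader with that expectation who can infer the arm could resolve borderline attempts in favour of the trained residents.

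The trained residents know what they received, so the operator cannot be masked. Outcome scoring can be, at least in part, because the event is on video and need not be judged at the bedside. What is at stake is the credibility of the Aim 1 comparison.

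**Working it through.** The plan gives no figure for reader bias, so there is nothing to reproduce. The main check is whether the stated workflow leads from label to arm.

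**Step 1: from label to arm**

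| Link | Source | Result |
|---|---|---|
| Video to date | Protocol, pg. 4 workflow | Date, time and bed space are on the label |
| Date to month | Immediate | Calendar month known |
| Month to arm | Protocol, Methods and Abstract | Known to anyone with the schedule; if alternation is strict, one known month gives all the others |
| Anything that breaks the chain | Protocol and SAP, read in full | None found; the participant code covers documents, not videos |

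Two details strengthen the link. The label has no resident identifier, so someone must match date and time to a resident to pick out participants' videos, and the plan does not separate that task from scoring. Methods also describes data collection as ongoing through each rotation. If scoring is done then, every clip in hand comes from a single arm.

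**Step 2: illustration of a false difference (all inputs assumed)**

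Let *s* be the share of attempts that are borderline. Suppose a reader who infers the arm scores 65% of these as successes in the intervention arm and 35% in the control arm, where an even-handed reader would score 50% in both.

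False difference = *s* × (0.65 − 0.35) = 0.30 × *s*

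- *s* = 0.05: 0.30 × 0.05 = 0.015, or 1.5 percentage points
- *s* = 0.20: 0.30 × 0.20 = 0.060, or 6 percentage points

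**Step 3: what a tilt inside that range would do to the test (assumed inputs)**

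Assume no true effect, one binary result per resident, independent residents, a two-sided test at 0.05, and a true success rate *p* of 40% to 67%. The scored rates are then *p* in control and *p* + *b* in intervention, with *b* = 0.05. The sizes are 27 per arm (Evaluation Plan) and 40 per arm (half of the 80 residents expected to enrol, Methods).

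Chance of a significant result favouring intervention = Φ[(*b* − 1.96 × SE0) / SE1], where SE0 uses the pooled rate and SE1 the two separate rates.

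Worked case, *p* = 0.50 and *n* = 27:

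- SE0 = √(2 × 0.525 × 0.475 / 27) = 0.1359
- SE1 = √((0.50 × 0.50 + 0.55 × 0.45) / 27) = 0.1357
- (0.05 − 1.96 × 0.1359) / 0.1357 = −1.59, giving Φ ≈ 0.055

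Across *p* = 40% to 67% the result is about 6% with 27 per arm and about 7% with 40 per arm, against a nominal 2.5% on that side. The calculation ignores clustering by month and repeated attempts by the same resident. It shows only that a modest tilt would matter, not that one is present.

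**The case against.** The strongest case against rests on what the documents leave open.

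- **Knowledge of the arm is not stated.** A reader might infer that whoever scores the videos knows the arm and that the outcomes are read unmasked. The documents are silent on masking, and nothing says that Safety Committee members hold the schedule. This stands: the supportable statement is that the arm can be inferred and that no masking is provided for.
- **The source of the outcomes is not spelled out.** Methods says that data will be collected and then describes video review. The recording is also described as part of quality improvement. Video scoring is the natural reading, since participants' videos get an additional review, but the plan does not say so outright.
- **The outcomes are fairly objective.** First-attempt success and attempt counts leave limited room for judgement. This stands as a limit on the likely size, but undefined attempt boundaries and an undefined clock leave some room.
- **This is not the only masking available.** A reader might think so, but the assessor of the simulation tests and the data analyst could also be masked.
- **A reader might infer that the instructor also scores.** Methods has intervention residents "Complete a hands-on intubation simulation with [name] instructing", but the names are removed, so overlap with the reviewers can be neither shown nor ruled out.
- **Recoding may not fully mask.** The camera is above infant and staff, so a resident may be recognised, and a reader may already have seen the dated clip. This stands and shapes the fix.

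None of these points supplies the missing safeguard.

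**Conclusion.** The concern holds in this form: arm follows month, videos are stored and opened under a date label, and nothing in either document keeps a reader who knows the schedule from inferring the arm while judging the Aim 1 live outcomes. This goes beyond a missing detail, because following the workflow as written makes the inference possible, while masked scoring of the same recordings is a practical alternative.

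Bias is possible, not shown. Its size cannot be derived from the documents: the 1.5 to 6 points rest wholly on the assumed borderline share and 65/35 split, and the false-positive figures on the further assumptions listed with them. The common direction across outcomes follows from the assumed favouritism and is not a finding. Nor is this a claim about a primary outcome, since none is named, or about analysed seconds, since timing enters the listed outcomes only through the 30-second limit. The point is a cheap improvement to the plan, not evidence that its results would be wrong.

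**What to change.** Amend the video-review text in Methods and the recording workflow on pg. 4 as follows.

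1. Existing study staff who do not score export each study clip under a random code, with date and time removed. Where feasible, they crop to the airway field so that the operator is not recognisable. Audio is kept if it is needed to confirm tube placement.
2. Clips from intervention and control months are pooled and scored in random order.
3. Scoring uses written definitions of attempt, success, and clock start and stop.
4. Scorers are those existing reviewers who do not hold the month-to-arm schedule, did not train the residents, and have not already seen the dated clip.
5. The coded scores are the trial outcome. The Safety Committee's dated quality-improvement review continues separately.

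**Cost.** A short protocol amendment; the work of finding and cutting clips from recordings that default to three hours; and scoring delayed until months of both arms can be pooled. Masking may remain incomplete if a resident is recognised. If no existing reviewer meets the conditions in step 4, the plan should state that scoring was unmasked and report this as a limitation.

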## **Study Population**

### Inclusion Criteria

Male and female residents from 18-89 years of age who have been assigned to the NICU for a monthly rotation are eligible to participate. At the beginning of all NICU rotations, all pediatric residents will be invited to participate in this research.

### Exclusion Criteria

Any pediatric resident who does not wish to participate

## **Risks and Benefits**

The only potential risk to study participants is the potential for loss of confidentiality. Measures to protect the confidentiality of study participants will be implemented as described in the Data Handling and Recordkeeping section below.

There will likely be direct benefits to the study participants to include enhanced instruction in neonatal intubation which would result in enhanced procedural skills for pediatric residents. Further, knowledge gained from the study could potentially benefit residents and community providers who are required to intubate, and their patients, in the future.

## **Data Handling and Recordkeeping**

The Principal Investigator will carefully monitor study procedures to protect the safety of research subjects, the quality of the data and the integrity of the study. A unique identifying code or number will be assigned to the participant's documents. In this way the data will remain anonymous. Only R. [name] and [name] will have access to study data and this data will be kept in a locked file in the principal investigator's office. [name] will routinely transcribe the data collected to an electronic file using the unique identifying code or number for each participant. The electronic file will be placed on a password protected file located on the UAMS Server. All recordings will be managed by a video recording server and stored on network accessible server storage space.

## **Evaluation Plan**

Using data from our previous intubation study using a manikin, we estimate a sample size for this study is 27 residents in each group. We recruited more than that for the manikin study, and for that study residents were required to come back for a post test. Thus, we anticipate no major difficulties in recruitment.

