Study Title: *“Manikin To Patient Intubation: Does It Translate?”*

Principal Investigator: R. [name].
University of Arkansas for Medical Sciences
[name]
[name]
[contact]
Email: [contact]

Study Location: University of Arkansas for Medical Sciences
[name]
[name]

Date: September 19, 2017

NCT number: NCT03046966

Statistical Analysis

Chi-square tests with the Benjamani-Holm p-value correction to account for test multiplicity will be used to analyze the difference in baseline measures and demographics. Chi-square testing will be utilized for comparing end of survey comfort. Logistic regression will be utilized to compare overall and first-time intubation success rates between the control and intervention groups. Logistic regression will be used to compare the difference in success rate between training level groups. To account for over-dispersion, a negative binomial regression will be utilized to assess difference in overall and first-time intubation success counts.

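### The SAP's logistic regressions of live intubation success name no unit of analysis and make no allowance for allocation by month or for repeated intubations by one resident

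*Protocol*

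**What the plan says.** On allocation, Protocol, Methods states: "Randomization will occur by the month the resident is assigned to the NICU". The Abstract adds: "The residents will receive training during alternating months". The month is therefore the unit of allocation, and all residents in a given month are in the same group.

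On data, Methods says that information is gathered through each resident's rotation. It includes "ability to successfully intubate on the first attempt, the total number of attempts to intubate" and the number of successes within the NRP time limit. No expected number of live intubations per resident is given.

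On analysis, the SAP states: "Logistic regression will be utilized to compare overall and first-time intubation success rates between the control and intervention groups". It then adds: "To account for over-dispersion, a negative binomial regression will be utilized to assess difference in overall and first-time intubation success counts". It names no month term, resident term, robust variance or unit of analysis for the logistic models. The negative binomial model has no month term either.

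On size, the Evaluation Plan states: "Using data from our previous intubation study using a manikin, we estimate a sample size for this study is 27 residents in each group". Methods says: "We anticipate 80 residents will enroll, similar to our previous study in which 82 residents participated".

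**The concern.** Residents who rotate in the same month share a calendar period and may share staff and case mix. Intubations by the same resident share that resident's skill. Both make results alike within a cluster. An ordinary logistic regression on individual intubations treats every result as independent, so it overstates the information about the group comparison.

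The trial exists because, in the protocol's words, "it is unknown if these skills will translate to live intubations". Both a positive and a null result must therefore be readable. With standard errors that are too small, a chance difference between months or between residents could pass for a training effect. An interval that is too narrow could also seem to exclude a gain that the data leave open.

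**Working it through.** **1. The plan's own figure.** The 27 per group (54 in total) cannot be reproduced, because outcome, control value, difference, variability, alpha, sidedness and power are all absent. Back-solving for a difference in means at two-sided 5%, d = (1.96 + z_power) × √(2/27):
- 80% power: (1.96 + 0.84) × 0.272 = 0.76
- 90% power: (1.96 + 1.28) × 0.272 = 0.88

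Many input sets fit, so 27 is neither confirmed nor contradicted.

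**2. Inputs for the analysis check.**
- From the documents: about 80 residents, so about 40 per group; allocation by month.
- Assumed: 7 months × 6 residents or 10 months × 4 residents per group; success 50%; k = 1 or 3 recorded intubations per resident; within-resident correlation ρ = 0.2 when k = 3; month ICC 0, 0.01 or 0.05; independent month effects; a two-sided 5% test.

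**3. Formula.** With m residents per month:

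Design effect DE = 1 + (k − 1)ρ + (m − 1) × k × ICC

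True type I error of the unadjusted test = 2 × [1 − Φ(1.96/√DE)]

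For k = 3, m = 6, ICC 0.05: DE = 1 + 0.40 + 0.75 = 2.15; 1.96/√2.15 = 1.34; type I error 18.1%. For m = 4: DE = 1 + 0.40 + 0.45 = 1.85; 15.0%.

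**4. Results.** Each cell gives m = 6, then m = 4. Simulations used 20,000 trials per setting with a nested beta-binomial model.

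| k | ICC | DE | Formula | Simulated, no cluster term | Simulated, resident-level t | Simulated, month-level t |
|---|---|---|---|---|---|---|
| 1 | 0 | 1.00, 1.00 | 5.0%, 5.0% | 4.9%, 5.5% | 5.6%, 5.5% | 5.0%, 5.3% |
| 1 | 0.01 | 1.05, 1.03 | 5.6%, 5.4% | 5-6% | not run | about 5% |
| 1 | 0.05 | 1.25, 1.15 | 8.0%, 6.8% | 7.7%, 7.8% | 8.5%, 7.8% | 5.1%, 5.5% |
| 3 | 0 | 1.40, 1.40 | 9.8%, 9.8% | 9.8%, 9.3% | 5.1%, 5.1% | 5.2%, 5.0% |
| 3 | 0.05 | 2.15, 1.85 | 18.1%, 15.0% | 17.9%, 14.1% | 11.4%, 8.9% | 4.8%, 5.1% |

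A resident-level analysis removes the repeat problem (row 4) but not the month problem (rows 3 and 5).

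**5. Intervals and power with a true 50% vs 65%, k = 3, ICC 0.05.** The unadjusted 95% interval covers the truth in 81% (m = 6) and 85% (m = 4) of trials; the month-level interval covers it in about 95%.

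For m = 6 there are 42 × 3 = 126 intubations per group:
- Unadjusted SE = √[(0.25 + 0.2275)/126] = 0.0616. Actual SE = 0.0616 × √2.15 = 0.0903.
- The unadjusted test rejects with probability Φ[(0.15 − 1.96 × 0.0616)/0.0903] = 63% (62% simulated). This is not valid power, because the type I error is 18%.
- The month-level test has non-centrality 0.15/0.0903 = 1.66 on 12 degrees of freedom (critical value 2.18), so power is 33%.

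For m = 4 (120 intubations; actual SE 0.0631 × √1.85 = 0.0858; 0.15/0.0858 = 1.75 on 18 degrees of freedom), month-level power is 38%.

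**6. Sensitivity to the form of the month effect.** I replaced independent month effects with a linear calendar drift of the same variance (0.05 × 0.25 = 0.0125) under strict alternation. With one intubation each, the unadjusted test stays at about 5%. The month-level t-test becomes conservative, at about 3% (about 2% with three each).

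**The case against.** The strongest reply is that the problem is conditional. No correlation, number of residents per month or number of intubations per resident appears in either document. The 14-18% figures need three intubations each, a month ICC of 0.05 and an intubation-level analysis all at once. With one result each and little month clustering, nothing is lost. The SAP leaves the unit unstated; it does not say that intubations will be treated as independent, and its negative binomial sentence shows that extra variation was considered. If month effects are a smooth trend, alternation already balances most of them. All of this stands, and it limits the size that can be claimed. It does not remove the gap, because a resident-level analysis still ignores the unit of allocation, and irregular month effects still inflate the error.

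A reader might infer that 27 per group is too few, or that it was sized on the wrong outcome. The documents do not support either. The inputs are unreported, not shown to be wrong, and the expected 80 residents would absorb a design effect of up to 80/54 = 1.48.

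A reader might also infer that the sizing should have allowed for repeated intubations. It need not. The sizing counts residents, and repeats add information per resident: 3/2.15 = 1.40 or 3/1.85 = 1.62 effective observations in the last row of the table, against 1. On the other hand, a surplus of residents protects power only; it does not correct the standard errors of an unadjusted model.

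**Conclusion.** The point holds for the SAP's logistic regressions and is minor. It is certain from the text that allocation is by month, that a resident can contribute several live results, and that the logistic models name neither a unit nor any term for month or resident. The over-dispersion provision does not reach them.

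The size is not certain. Under the assumed inputs, the true error of a nominal 5% test runs from no material excess (5-6%) to 14-18%. It would be wrong to quote the upper figure as a property of this trial. The two-sided 5% level and the 95% interval are conventional assumptions here, since neither document states them.

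**What to change.** In the SAP, name the unit of analysis for the logistic regressions and account for month, as the unit of allocation, and for resident within month. Either of these would do:
- month-level success proportions compared by a t-test with months minus 2 degrees of freedom; or
- GEE or mixed logistic regression with month as the cluster and a small-sample correction, which is needed because the assumed layouts give only 14 to 20 months.

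Report the difference in success with its 95% confidence interval. For completeness, the Evaluation Plan could also state the outcome and inputs behind the 27.

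The change adds a sentence or two of text. It needs no change to conduct and no new data, since the rotation month is already known. The price is precision. In the benign case (one result each, no clustering, 50% vs 80%), simulated power falls from about 82-84% to 78-79%. With three each and ICC 0.05, month-level power for 50% vs 65% is only about 33-38%. In that setting the mean 95% half-width under no difference is 18-20 points, against an unadjusted 12-13 that is too narrow. The month-level test can also be conservative if month effects follow a smooth calendar trend under alternation.
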